- Requires inpatient hospitalization or prolongation of existing hospitalization;
- Results in a persistent or significant incapacity or substantial disruption of the ability to conduct normal life functions;
- Important medical events that may not result in death, be life-threatening, or require hospitalization may be considered serious when, based upon appropriate medical judgment, they may jeopardize the subject and may require medical or surgical intervention to prevent one of the outcomes listed in this definition;

- SAEs will be reported regardless of their relationship to the study intervention.

d. SAE Monitoring and Reporting

Research subjects will be monitored at each study contact (i.e., phone call and follow-up clinic visits). Serious adverse events will be collected and recorded on the appropriate electronic case report form. Active monitoring of SAEs will begin as soon as a research subject signs the Informed Consent and will continue through end-of-study for each subject.

Serious adverse events require expedited reporting. Expedited reporting is defined as the completion and submission of the appropriate electronic case report form to the study's DataFax system within three (3) business days of the Local Site Investigator being aware of the SAE. The Study Pharmacist (or designee) is responsible for evaluating all SAEs for subject safety concerns by the close of business the next day after receipt of the SAE.

e. Reporting Serious Adverse Events to the Data Monitoring Committee (DMC)

The Perry Point CSP Center and CSP Clinical Research Pharmacy Coordinating Center will prepare aggregated SAE reports for the DMC annually or on a schedule set by the Committee.

D. Missed Visits

If the subject fails to come to the clinic for the six-week follow-up visit, the research coordinator at the site will call the subject on the same day or, at the latest, the next working day to inquire about the reason for the missed visit and to reschedule the subject's appointment as soon as possible. The research coordinator will continue trying to contact the subject until the subject receives an appointment or formally withdraws from the study. If the subject still refuses, the research coordinator will try to complete as much of the six-week assessments as possible on the phone by interview and/or by mail (e.g., the VR-12, Seattle Angina Questionnaire).

E. Termination

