All subjects will be followed up actively until the sites are decommissioned. After the six-week clinic visit, each subject will be contacted by phone, every three months, to collect information on any MACE event, leg wound status, etc. If the subject cannot be contacted, his/her CPRS records will be assessed to check for any MACE event. If the subject dies or refuses to continue participation, he/she will be terminated. A termination form will be used to record the termination information for these subjects. At the end of the active follow-up phase (approximately 4.5 years from study start-up) each continuing subject's status will be recorded in a termination form to indicate official termination of the active follow-up phase of the study.

All subjects terminated from the active follow-up phase of the study will be continually followed by the study's national nurse coordinator where existing VA administrative databases will be mined for MACE for another two years (passive follow-up phase).

XI. Quality Control Procedures

A. Standardization/Validation of Measurements

Prior to the start of the study enrollment, all of the site investigators, harvesters and research coordinators will be provided with in-depth trainings on different aspects of the conduct of the study during a “kick-off” meeting to ensure proper understanding of the technical aspects of the protocol, to ensure uniformity in the completion and submission of the case report forms and to ensure uniformity in implementing and performing the study procedures.

During this meeting, the site investigators and harvesters will receive a half-day of Good Clinical Practices (GCP) training and the research coordinators will receive one day of GCP training. If any of the research coordinators from the participating sites is unable to attend the kick-off meeting, a repeat GCP training will be arranged. The GCP trainings will be provided by the SMART team from the Pharmacy Coordinating Center, Albuquerque, New Mexico. In any event, until this training is completed, the sites will not be allowed to begin randomization for the study.

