4. Did the subject have an acute myocardial infarction since the last contact? No Yes
If yes, (complete form 15 and 19)
a. AMI Date

--	--

--	--

--	--	--	--	--

Month Day Year

5. Did the subject receive PCI since the last contact? No Yes
If yes,
a. Procedure Date

--	--

--	--

--	--	--	--	--

Month Day Year

6. Did the subject receive CABG since the last contact? No Yes
If yes,
a. Procedure Date

--	--

--	--

--	--	--	--	--

Month Day Year

For Q 3-6 answered yes, obtain appropriate medical records for required source documentation.

VISIT (Months)

--	--

SITE NO.

--	--	--

SUBJECT ID

--	--	--	--

ALPHA CODE

--	--	--	--

MEDICATIONS

7. Has the subject taken any of the following medications since last contact or review?

a. Beta blocker	No 	Yes 
b. ACE/ARB Inhibitor	No 	Yes 
c. Statin	No 	Yes 
d. Non-Statin LLA	No 	Yes 
e. Nitrate	No 	Yes 
f. Calcium Channel Blocker	No 	Yes 
g. Aspirin	No 	Yes 
h. Plavix	No 	Yes 
i. Warfarin	No 	Yes 

Form Completed By _____ Date _____

VISIT NO.	SITE NO.	SUBJECT ID	ALPHA CODE	DATE OF ASSESSMENT																							

 	 	

			

 	 	 	

				

 	 	 	 	

					

 	 	 	 	

					

 	 	

			

 	 	

			

 	 	 	 	

				
				Month	Day	Year																					

FORM 14 – STUDY COMPLETION/TERMINATION

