6.7 Serious Adverse Events

Serious adverse event (SAE) incidence using MedDRA coding after randomization will be reported by body system and preferred term, overall and by treatment (TABLE 23).

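### The protocol requires SAE monitoring and leg-wound enquiry at every phone call, but the call form has no item for either, and its PCI and CABG items do not prompt an SAE report

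*Protocol*

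**What the plan says.** Protocol X.C.d sets the duty: "Research subjects will be monitored at each study contact (i.e., phone call and follow-up clinic visits". It also fixes the period: "Active monitoring of SAEs will begin as soon as a research subject signs the Informed Consent", running to the end of study for each subject. The definition in X.C.c includes "Requires inpatient hospitalization or prolongation of existing hospitalization", and its list ends by stating that "SAEs will be reported regardless of their relationship to the study intervention".

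X.E (Termination) says that after the six-week visit "each subject will be contacted by phone, every three months, to collect information on any MACE event, leg wound status, etc". X.B (Interim Follow-Up) describes the same calls as covering cardiac problems and procedures, including a clinically indicated catheterization. It mentions neither SAEs nor the leg wound.

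Form 12 (Appendix E) is the form for these calls. After date and contact status it asks about death, MI and PCI. Its last event question is "Did the subject receive CABG since the last contact", followed by a procedure date. A list of nine drug classes ends the form.

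SAP 6.7 states that SAE incidence "will be reported by body system and preferred term, overall and by treatment" in Table 23, and SAP 8 says that information on all SAEs will be collected.

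**The concern.** The text promises more than the form can hold. Take, for illustration, a subject admitted with a stroke in month 7, or one whose harvest wound reopens in month 4. Each could truthfully answer no to every event item on Form 12, and nothing on the page would lead the coordinator to Form 15.

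At stake is how even and complete the by-arm SAE comparison is. Adverse event incidence by arm goes to the DMC and into the primary manuscript (Protocol Appendix D; SAP 5.5.1). If the question is left to each site, the answer may vary with who asks, how they ask, and whether they know the arm. Wound trouble is the recognised drawback of open harvest, and X.E's undertaking to follow it by phone has no field behind it.

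**Working it through.** The plan gives no figure to reproduce here, and no arithmetic applies beyond counting items. The check sets the protocol text beside the forms.

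| Matter | Protocol text | Form 11 (six weeks) | Form 12 (each call) |
|---|---|---|---|
| Death | SAE (X.C.c) and MACE | Asked; Form 15 | Asked; Form 15 |
| MI | MACE; SAE if X.C.c met | Asked; Form 15 | Asked; Form 15 |
| PCI | MACE; SAE if admitted | Asked, dated; no Form 15 | Asked, dated; no Form 15 |
| Repeat CABG | MACE; SAE if admitted | Asked, dated; no Form 15 | Asked, dated; no Form 15 |
| Catheterization | X.A and X.B | No item | No item |
| Other admission or serious event | X.C.c and X.C.d | No item | No item |
| Leg wound | X.E, for the calls | Form 10 at the same visit | No item |

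1. **Count.** Form 12 has 4 event items. Two instruct the site to complete Form 15, two do not, and none covers other admissions, other SAEs, the wound or catheterization. Form 11 has the same four event items with the same pattern.

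2. **PCI and CABG.** XI.B (Subject Management) gives major adverse cardiac events as its example of SAEs, and XVII.D.2 makes revascularization a MACE component. The missing Form 15 instruction therefore sits badly with the protocol's own example as well as with the hospitalization criterion.

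3. **Other forms.** Form 10 item 9 (stay beyond 14 days) does lead to Form 15, but Table 2 schedules Form 10 only at discharge and six weeks. Form 13 is scheduled only at Visit 49. Form 15 is as needed. None of these places a prompt at the routine three-monthly calls.

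4. **Fallback.** When a subject cannot be reached, X.E has the medical record checked for MACE. It does not mention other SAEs.

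5. **Who asks.** Under Appendix D the research coordinator places the randomization call and receives the assignment. Under X.B the site study coordinator makes the follow-up calls. Removal of arm information is described for the Clinical Events Committee packets (XV.A), and by-arm outcome data are withheld from the study group (Appendix D). No masking of subjects or site staff is described, and SAP 3.4, despite its heading, describes no blinding.

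**The case against.** The strongest reply is that Form 12 is a data-capture form, not an interview script, and that the duty to ask is set elsewhere. X.C.a makes the investigator responsible for close monitoring for new SAEs. XI.B has coordinators ask by phone about health status and seek records of outside hospital care. SAE reporting is a training session (XI.A), failure to monitor for SAEs is noncompliance code 03 on Form 18, and central quality assurance may cover safety reporting (XV.A). PCI and CABG are asked about, dated and backed by medical records, and the DMC sees revascularization through the primary endpoint.

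Most of this stands. A reader might infer that Table 23 rests on whatever patients volunteer. The documents do not support that: death, MI and the Form 10 prolonged stay are asked about and lead to Form 15, and enquiry about the rest is required. But none of these provisions supplies a question, or a field showing that it was asked.

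A reader might also try to size the gap by applying ROOBY's one-year revascularization rates (6.7% EVH, 3.4% OVH; Protocol II) to 575 per arm: 575 × 0.067 ≈ 39 and 575 × 0.034 ≈ 20. Those would be patients with procedures, not missing SAE reports. They would measure a gap only if no site filed Form 15 for an event it had just recorded. The rates also come from ROOBY's one-year catheterization subset (894 of 1,471), whereas REGROUP's Table 2 schedules no follow-up angiography. Counting calls made without the question likewise counts calls, not missed events.

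On wound harm, the prespecified assessments are at discharge and six weeks, in a window of 4 to 8 weeks. Form 10 covers antibiotics, drainage, debridement and dressing visits. No endpoint uses later wound data.

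**Conclusion.** The mismatch holds. The protocol requires SAE monitoring at every call and says the calls collect leg wound status, yet Form 12 has no item for either, nor for the catheterization named in X.B. PCI and CABG carry no Form 15 instruction on Forms 11 or 12. For SAEs other than death, MI and the Form 10 prolonged stay, ascertainment for Table 23 rests on each site's unscripted enquiry by staff not described as masked.

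The consequence is limited. Differential reporting by arm is a possibility, not a finding, and the number of missed SAEs cannot be estimated from these documents. Table 23 is descriptive. The change is worth making because it is cheap; the trial's main results do not depend on it.

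The conclusion assumes that the Appendix E forms are those in use. Appendix D calls them drafts, and the SAP schedule later adds a Form 22. Form 13, the first part of Form 10 and the operations manual were not available, so a scripted question in the manual cannot be excluded. Forms 10 and 13 would not close the gap in any case, since neither is scheduled at the routine calls.

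**What to change.** - Add to Forms 11 and 12: *Any hospital admission or other serious event since last contact? If yes, complete Form 15.*
- Add a Form 15 cross-reference to the PCI and CABG items on both forms for cases meeting the SAE definition, or state in X.C that these procedures are exempt from SAE reporting.
- Add one leg-wound item to Form 12, or delete leg wound status from X.E. Reconcile the catheterization wording in X.A and X.B with the forms in the same revision.
- State in SAP 6.7 how Table 23 events were ascertained. This matters most if calls have already been made on the present form, because new items will not cover them.

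The cost is a form revision with a notice to coordinators, about one minute per call, and higher reported SAE counts. The DMC should be told to expect that rise.

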All participating vein harvesters must meet the minimum EVH/OVH volume criteria [at least 100 EVH cases with low conversion rates (<5%) as part of an EVH program established for more than two years] to be eligible to enroll subjects in this study. Unless an urgent medical condition exists, the subject's surgery will be scheduled to occur at the earliest possible date based on expert harvester availability and other center circumstances. The randomization procedure will occur after the participating expert harvester is assigned to the subject. Subjects will be randomized within the assigned participating harvesters to one of the two study harvesting technique arms (EVH or OVH).

Recognizing that the subject's assignment to a participating vein harvester will have already occurred, the study randomization to either EVH or OVH will be done by a telephone call to the Perry Point Cooperative Studies Program Coordinating Center (CSPCC). A block randomization scheme will be used to randomize subjects in two treatment groups. A random sequence of block sizes will be used to reduce the chances of guessing future allocations.

C. Subject Assessments

Baseline assessments will be collected prior to surgery and randomization including Body Mass Index, Ankle-Brachial Index and Venous Clinical Severity Scale. Intraoperative assessments will be collected during the CABG procedure, 24 and 48 hours postoperatively as well as assessments at the time of hospital discharge or 30 days post-surgery, whichever occurs first. Subjects will return for a six-week clinic visit to assess the condition of their leg incision and healing status. Any necessary medical care required will be administered per the Institution's standard practice.

Subjects will receive a phone call every three months for follow-up for events until subject termination. Subjects will complete QoL surveys again at one year either by telephone or mail. If the subject reports a major adverse cardiac event (e.g. MI, repeat revascularization) after discharge from the hospital, then records will be obtained for final adjudication. Ascertainment for death will include review of VA central databases.

Following is a list of assessments/study details that we plan on collecting:

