19 – Confirmation of MI by Local Site														X
20 – Confirmation of MI by Clinical Events Committee														X
21 – Cause of Death by Clinical Events Committee														X
86 - Consent	X													

* Form 10 is collected at two time points (discharge and 6 weeks), do not fax form until the six week assessment has been completed.

CSP #588
RANDOMIZED ENDO-VEIN GRAFT PROSPECTIVE – REGROUP TRIAL
 Version 1.2 Protocol
 October 1, 2013

X. Post-Discharge Follow-up Assessments

A. Six Week Visit

Subjects will be assessed for leg wound complications approximately 6 weeks post-surgery during a clinic visit (this visit will take place between 4 weeks to 8 weeks post-surgery). Problems and/or procedures related to their cardiac health (i.e., acute myocardial infarctions, revascularization procedures, or a clinically indicated cardiac catheterization) will be obtained, Self-assessment satisfaction survey will be repeated at this time as well as Quality of Life questionnaires. Any necessary medical care required will be administered per the Institution's standard practice.

B. Interim Follow-Up

Every three months during the active follow-up period post-surgery, the site study coordinator will contact the study subjects by telephone to determine whether they have experienced any problems and/or procedures related to their cardiac health (i.e., acute myocardial infarctions, revascularization procedures, or a clinically indicated cardiac catheterization). These interim calls will collect MACE data, maintain rapport with subjects and let them know that the study team at the sites is interested in their progress. At one year the subject will complete QoL surveys by telephone or mail.

C. Monitoring Serious Adverse Events

a. Role of the Local Site Investigator in Reporting Serious Adverse Events (SAE)

The local site investigator is responsible for following CSP reporting requirements:

- Complying with the study procedure for reporting serious adverse events;
- Reviewing the accuracy and completeness of all SAEs reported; and
- Closely monitoring research subjects for any new SAEs.

b. Study Intervention

For the purpose of this study, the intervention for this study is defined as the *vein harvesting procedure for a saphenous vein graft in coronary artery bypass*.

c. Definition of a Serious Adverse Event (SAE)

A serious adverse event is an adverse event that results in one of the following outcomes:

- Result in death;
- Is life-threatening;

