All data will be stored within the VA firewall and will be password protected at all times. Hard copy data will be sent via a traceable mail system (i.e., UPS), via a courier, or via secure fax. Access to these secure fax servers is restricted to the VA Perry Point coordinating center personnel with approved access to the system. All secure fax servers are compliant with VA directive 1605.1 and 6500. All data security incidents will be reported in accordance with VA policy within one hour of discovering the incident to:

- The District (local) Information Security Officer (ISO)
- The VA Perry Point CSPCC Data Security Officer
- The local IRB.

Administrative and healthcare utilization data on consenting participants will be extracted from the VA national database resources. The VA national data resources include, but are not limited to: the National Patient Care Database (OPC, PTF), VA-Medicare/Medicaid merge, national Laboratory and Pharmacy extracts (DSS, PBM), Corporate Data Warehouse (Health Data Repository), Medical Domain Web Services (MDWS), Patient Care Services Clinical Data Warehouse, Surgical Care Improvement Project (SQIP), Surgical Quality Workflow Manager (SQWM), VA Computerized Patient Record System (CPRS), Veteran Informatics and Computing Infrastructure (VINCI), VHA Support Service Center (VSSC), VA Surgery Quality Improvement Program (VASQIP), and the VA Vital Status File. Additionally, IT and Informatics initiatives to build the tools that will allow electronic medical record data extraction are being developed and will be used to obtain VISTA-level data to enhance the breadth of information and disease characterization that is lacking in the current national databases. This data will be downloaded/transferred with the appropriate permissions for use of these VA national databases, or individual VA Medical Centers, to the VA Central Research Database.

E. Data Sharing Plan

After the main results of this study have been published, de-identified data from this study may be shared with other VA investigators, other Federal health agencies, or academic institutions for the purpose of additional analyses provided this use has been approved by the appropriate VA oversight committee and there is an agreement in place that defines the limits of this use.

XIII. Feasibility of the study within the VA System

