MACE, the composite endpoint that includes Death (all cause), Myocardial Infarction (MI) and Revascularization for myocardial ischemia, will be the primary outcome measure after randomization and the index CABG. Each randomized subject (either in Endoscopic or in Open harvesting group) will be followed after the index CABG to capture the time-to-MACE event where an ‘EVENT’ will be defined as either death (all cause) or an MI or a revascularization procedure during the follow-up period. Total follow-up period will be 6.5 years of which the first 4.5 years will be active follow-up (using in-clinic visit or by telephone) period and will be carried out by the site personnel. The remaining 2 years will be passive follow-up which will be carried out centrally by the chair’s office staff using the VA patient database. A minimum of 1 year of active follow-up will be used for subjects who will be randomized at the tail end of the 3-year projected enrollment period of the study. The subjects

who will either be lost to follow-up or will not experience an 'EVENT' before the end of the follow-up period will be considered as right censored.

The primary analysis of such time-to-Mace event data will include the events only from the active follow-up period (which is 4.5 years). The secondary analysis will include events from the entire 6.5 years of follow-up period.

Survival analysis techniques will be used to analyze the time-to-MACE event data for both primary and secondary analyses.

Kaplan-Meier analysis, a nonparametric method, will be used to estimate the survival (not experiencing MACE) over time in the two harvesting groups and a log-rank statistic will be used to test the equality of the survival function estimates in the two groups (the null hypothesis).

Cox's Proportional Hazards models will be used to investigate the effect of harvesting technique on the time until MACE adjusted for other potential influential variables, such as, age, gender, harvester's experience etc.

3. Secondary Outcomes Measures

One and Three-year MACE: This composite endpoint consists of

- i. Death (all cause);
- ii. Myocardial Infarction and
- iii. Revascularization for myocardial ischemia.

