RANDOMIZED ENDO-VEIN GRAFT PROSPECTIVE – **REGROUP TRIAL**

Version 1.2 Protocol

October 1, 2013

outcome measures, the statistical techniques for the analyses and the table shells in which the results of the analyses will be presented in the reports.

Primary Outcome Measure:

Time-to-MACE event: MACE, the composite endpoint that includes Death (all cause), Myocardial Infarction (MI) and Revascularization for myocardial ischemia, will be the primary outcome measure after randomization and the index CABG. Each randomized subject (either in Endoscopic or in Open harvesting group) will be followed after the index CABG to capture the time-to-MACE event where an 'EVENT' will be defined as either death (all cause) or an MI or a revascularization procedure during the follow-up period. Total follow-up period will be 6.5 years of which the first 4.5 years will be active follow-up (using in-clinic visit or by telephone) period and will be carried out by the site personnel. The remaining 2 years will be passive follow-up which will be carried out centrally by the chair's office staff using the VA patient database. A minimum of 1 year of active follow-up will be used for subjects who will be enrolled almost at the tail end of the 3-year projected enrollment period of the study. The subjects who will either be lost to follow-up or will not experience an 'EVENT' before the end of the follow-up period will be considered as right censored.

The primary analysis of such time-to-MACE event data will include the events only from the active follow-up period (which is 4.5 years). The secondary analysis will include events from the entire 6.5 years of follow-up period.

Survival analysis techniques will be used to analyze the time-to-MACE event data for both primary and secondary analyses.

Kaplan-Meier analysis, a nonparametric method, will be used to estimate the survival (not experiencing MACE) over time in the two harvesting groups and a log-rank statistic will be used to test the equality of the survival function estimates in the two groups (the null hypothesis).

Kaplan-Meier curves for all other predictors, e.g., age, gender etc., will also be plotted to provide insight into the shape of survival function for each group. These curves will also provide information about the proportionality among the groups (i.e., whether the curves are parallel or not).

[figure not shown]

Figure 3: Typical Kaplan-Meier curve comparing two treatment groups

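### In active follow-up, a reached subject's negative answer about MI or revascularization triggers no required record check, so unreported non-fatal events may be missing from the primary analysis

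*Protocol*

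**What the plan says.** The primary outcome is time to first MACE, where "an 'EVENT' will be defined as either death (all cause) or an MI or a revascularization procedure during the follow-up period" (Protocol Appendix D; likewise Section XVII.D and SAP 2.2.1). The primary analysis uses active-phase events only, about 4.5 years. The two-year passive phase enters a secondary analysis.

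After discharge, the active-phase sources are:

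- **Subject reached.** A site coordinator telephones every three months (Protocol X.B). Protocol IX.C states: "If the subject reports a major adverse cardiac event (e.g. MI, repeat revascularization) after discharge from the hospital, then records will be obtained". Form 12 in Appendix E carries the same trigger: "For Q 3-6 answered yes, obtain appropriate medical records for required source documentation". Form 11, used at six weeks, works the same way.
- **Subject not reached.** "If the subject cannot be contacted, his/her CPRS records will be assessed to check for any MACE event" (Protocol X.E).
- **Potential drop-out.** MACE is sought in VA databases (Protocol XVII.G, SAP 5.3).
- **Death.** VA central databases are reviewed, with no condition on phone contact (Protocol IX.C).

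Mining VA databases for MACE in all subjects is described for the passive phase (Protocol X.E, XI.B). Separately, Protocol XII.D says: "Administrative and healthcare utilization data on consenting participants will be extracted from the VA national database resources". That sentence is not tied to MACE, to a study phase or to a schedule.

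**The concern.** A negative phone answer about MI or revascularization ends the inquiry for that quarter unless something else brings the event to the site's notice. A subject who was not reached gets a chart review for the same quarter. Two subjects with the same unreported MI can therefore be classified differently because of how the contact went.

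The Clinical Events Committee does not close this gap. It confirms MIs that have been reported to it (Protocol XV.A), so it removes false positives but cannot recover false negatives. Nothing says that the passive-phase search looks back before that phase began.

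Three things are at stake: the number of primary events; the absolute differences on which SAP 7.2 judges H2 (6 points at one year, at least 8 at three years); and comparability between arms if reporting differs by arm. On the last, the research coordinator receives the assignment at the randomization call (Appendix D), a site coordinator makes the follow-up calls, and no passage blinds the caller or the subject.

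**Working it through.** **1. Reproduce the plan's figures (Protocol XVII.B).**

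- *Time-to-MACE:* event-free 83.5% EVH and 91.5% OVH, 97.5% power, two-sided 5%. HR = ln(0.835)/ln(0.915) = 2.03. Freedman's formula gives events = (1.96 + 1.96)² × [(2.03 + 1)/(2.03 − 1)]² = 133. The mean event rate is (16.5% + 8.5%)/2 = 12.5%, so N = 133/0.125 = 1064, or 532 per group. This matches the plan.
- *One-year MACE:* 15.5% and 9.5%, 85% power. The pooled two-proportion formula gives 545 per group. This also matches.

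The stated sample sizes are correct for fully captured events.

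**2. Effect of equal under-reporting.** Let f be the non-fatal share of first events and m the share of those that are missed. Deaths are taken as fully captured. The share of events retained is k = 1 − f × m.

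The documents do not give m; 5–30% is assumed. For f, the registry analysis cited in Protocol Section II (EVH group, three years) gives a floor of (19.5 − 13.2)/19.5 = 32%. The upper end of 80% is assumed.

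For the primary comparison, events = 1064 × 0.125 × k, the HR is recomputed as ln(1 − 0.165k)/ln(1 − 0.085k), and power = Φ(√events × (HR − 1)/(HR + 1) − 1.96). For one-year MACE, both rates are multiplied by k at 545 per group.

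| f | m | k | Primary events | Primary power | One-year difference | One-year power |
|---|---|---|---|---|---|---|
| – | 0 | 1.000 | 133 | 97.5% | 6.00 points | 85% |
| 32% | 5% | 0.984 | 131 | 97.3% | 5.90 | 84.4% |
| 32% | 30% | 0.904 | 120 | 95.9% | 5.42 | 80.8% |
| 50% | 20% | 0.900 | 120 | 95.9% | 5.40 | 80.6% |
| 80% | 5% | 0.960 | 128 | 96.9% | 5.76 | 83.4% |
| 80% | 30% | 0.760 | 101 | 92.0% | 4.56 | 72.9% |

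A true three-year difference of 8 points would be observed as between 8 × 0.984 = 7.9 and 8 × 0.76 = 6.1 points. The table treats a missed event as lost. A subject with a later reported event or death would still count, only later, so for a given m the loss is if anything overstated.

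**3. Bias between arms.** Take a true rate of 12.5% in both arms.

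- *Answering differs by arm:* the spurious difference is 12.5 × f × (difference in answering) × (difference in sensitivity between phone and chart review). With f = 32–80%, answering differing by 5–10 points and sensitivity by 15–20 points, it runs from 12.5 × 0.32 × 0.05 × 0.15 = 0.03 to 12.5 × 0.80 × 0.10 × 0.20 = 0.20 percentage points.
- *Reporting differs by arm:* the spurious difference is 12.5 × f × (difference in reporting). With a difference of 5–10 points, it runs from 12.5 × 0.32 × 0.05 = 0.2 to 12.5 × 0.80 × 0.10 = 1.0 percentage points.

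These differences between arms are illustrations. The documents give no evidence that either exists.

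**The case against.** The strongest reply is that patient recall is far from the only route. Perioperative MI is sought by 12-lead ECG on the first two postoperative days, with biomarkers if triggered (Protocol IX.C, XI.B). Every inpatient hospitalization is a serious adverse event whatever its cause, and the reporting clock starts when the investigator becomes aware (X.C). Form 12 may be completed from chart review. Sites are to make all efforts to obtain information from non-study hospitals (XI.B). Form 13, the MACE Event Form, is scheduled at month 49, and its content is not in the available text.

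Much of this stands, and it rules out several stronger readings:

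- *That negative answers are never checked, or that events are certainly lost.* The documents are silent rather than prohibitive, and Protocol XII.D permits extraction for all consenting participants.
- *That the whole composite depends on who answers.* Death has its own database review, so the gap is confined to non-fatal MI and revascularization after discharge.
- *That the primary analysis becomes underpowered.* It stays at 92% or more across the assumed range.
- *That knowing one's arm from the leg scar biases the result.* Nothing in the documents shows that it changes reporting of an MI or PCI.

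The reply does not supply a required check. Adverse events are monitored at study contacts, which is largely the same channel. The effort for outside hospitals has no stated way to learn of a visit the subject does not mention. The general extraction is not assigned to endpoint ascertainment.

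**Conclusion.** The point holds in limited form. After discharge in the active phase, the plan requires no record check for non-fatal MI or revascularization when a reached subject reports none, yet it specifies one for uncontactable subjects and potential drop-outs. Capture therefore depends on the route of contact, and unreported non-fatal events may be absent from the primary analysis.

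Under equal under-reporting in the assumed ranges, primary power falls from 97.5% to about 97–92% and one-year power from 85% to about 84–73%. The relative effect is roughly unchanged, while the absolute differences used for H2 shrink to between 98% and 76% of their true size. The consequence is thus modest for the primary test and larger for the secondary one- and three-year comparisons. Bias between arms is possible because callers and subjects are not blinded, but its existence and size are unknown. All these sizes rest on assumed values of f and m; the only anchor in the documents is the 32% floor for f.

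**What to change.** State in Protocol X.E and SAP 5.3 and 7.1 that, at the end of the active phase, the already planned VA database and CPRS search for MI, PCI and repeat CABG is run for every randomized participant from the index CABG date, whether or not they were reached, with treatment arm removed from the search file. Send MI hits to the Clinical Events Committee. Confirm PCI and CABG hits from the procedure record, since the committee's stated remit covers only deaths and MIs. Count confirmed active-period events in the primary analysis at their event date.

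The cost is additional record review for the national nurse coordinator and additional adjudication for the existing committee; no visits are added. The search gives all subjects one common source for non-fatal events, but events treated outside the VA and not reported would still be missed.
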